Efficacy of a Novel Sleep Device to Promote Sleep Continuity in Infants

Protocol Prepared by:
[name]

NCT05078112

Document Date: March 28, 2022

[figure not shown]
Study Purpose: Objectives and Hypothesis to be tested

The study will evaluate whether use of a novel sleep device in the form of a crib mattress for one month improves sleep metrics in infants aged 2 months to 12 months. Sleep metrics will include both objective measures of sleep captured by the device as well as parent report.

The hypothesis is that use of the sleep device over one month will lead to improved sleep quantity and quality.

Background and Significance

Behavioral insomnia of childhood due to sleep-onset associations is a well-studied clinical entity. The science behind infant insomnia explains why some children wake up repeatedly at night. Based on what we know about sleep, the term “sleeping through the night” is a misnomer. No human being actually sleeps through the night, infants included. Nighttime sleep occurs in cycles in which we dive into deeper stages of sleep, then emerge into lighter stages at the end of the cycle. The cycle lasts about 60 minutes for infants and 90 minutes for adults.¹ There is often an awakening at the end of a sleep cycle during light sleep. Here is a simplified diagram:

An infant that “sleeps through the night” is able to simply go back to sleep during the *normal* awakenings at night. However, an infant with sleep onset association disorder is unable to fall back asleep. This sleep disorder is termed behavioral insomnia of childhood, sleep-association subtype by the International Classification of Sleep Disorders.² It involves difficulty sleeping through the night due to needing caregiver involvement to transition from awake to asleep. For example, if a parent consistently rocks an infant during the process of falling asleep at the beginning of the night, the infant learns to associate the transition of falling asleep to that particular intervention. The rocking is the sleep association for the child. When the infant awakens at night during a normal awakening, the infant begins to cry until rocked to sleep once again. This happens repeatedly through the night, often times separated by an hour (the time it takes to go through another sleep cycle). It leads to disruption to both the infant and parent’s sleep.

Treatment of sleep onset associations can start as early as four months of age and often involves techniques known as “extinction” or “modified extinction”. Both techniques have a great deal of sleep research to support safety and efficacy.³ The American Academy of Sleep Medicine has a practice parameter recommending these treatment techniques.⁴ However, implementation of these techniques is challenging due to infants/toddlers crying regularly during the process and the stress it creates in caregivers. Many parents give up and subject both themselves and their children to months (and sometimes years) of poor sleep as a result, which has a myriad of health consequence. In contrast,

successfully implementing a strategy to help a child sleep leads to a multitude of benefits, including improved behavior in the child, improved mood in adults, and even better marital satisfaction for caretakers.⁵

The problem is quite common, with estimates of 20-30% of young children experiencing sleep challenges.³ Infants between the ages of six months to one year are particularly susceptible to sleep difficulties, with 25-50% still awakening at night.⁶ A straight-forward, safe solution with ease of application, decrease in level of child distress, and proven efficacy is vital to help young children get the sleep they need.

The device in this project works by detecting when a child is awake, produces a sound and motion to soothe a child back to sleep (thereby creating a new sleep association), and then over the course of weeks, weans the child from this new association by decreasing the output from the device based on sensor input and the internal algorithm of the device. This would slowly teach a child to self-soothe, thereby allowing for more continuous sleep.

Research Design and Procedures

The study will be a prospective trial with subjects serving as their own internal controls. Goal enrollment is 20 children over the course of six months. Goal enrollment is based on an *a priori* power analysis performed by a Duke biostatistician.

Schedule of Events:

1. Screening visit/Consent

Data collection at screening visit:

DOB

Weight

Height

Past Medical History

Medications

Household members, including number of siblings and age

Sleep environment: Where does child sleep at night? Does the child use a crib?

Prior trial of sleep training: What methods used and how long?

Inclusion/Exclusion criteria reviewed

Caregiver consented

2. Day 1 of study

a. Mattress delivery – Program coordinator meets family at mutually agreed upon location and give them mattress and instructions on use.

b. Family fills out questionnaires to obtain baseline metrics via Qualtrics

3. Day 5 of study – check-in call from study team to ensure everything going well and answer any questions.

4. Day 15 of study – check-in call from study team to answer any questions.

5. Day 30 – mattress returned to study coordinator. Parents fill out questionnaire via Qualtrics

Metrics captured by the device via micro SD card:

1. Number of minutes of crying at night
2. Number of minutes of wakefulness
3. Number of minutes of wakefulness between time asleep and time awake
4. Number of minutes of quiet wakefulness
5. Number of minutes of quiet wakefulness between time asleep and time awake
6. Number of total discrete crying episodes
7. Total length of time asleep
8. Total length of time in crib
9. Sleep latency

Parent reported metrics at baseline and end of study measured via Qualtrics survey:

1. Number of times parents report crying per night
2. Number of times child is removed from crib per night
3. Parent's self-reported length of child's sleep
4. Parent's rating of the child's sleep quality
5. Parent's rating of the child's daytime behavior
6. Parent's self-reported subjective sleepiness - Epworth Sleepiness Scale (ESS)
7. Parent rating of bonding with child
8. Parent mood and stress scale
9. Parent depression scale

Selection of Subjects

Inclusion criteria:

- 1) Age between 2-12 months.
- 2) Meets clinical criteria for behavioral insomnia of childhood, sleep association subtype, as defined by the International Classification of Sleep Disorders Manual.

Exclusion criteria:

- 1) Diagnosed comorbid health problem that may disrupt sleep.
- 2) History of birth prior to 37 weeks gestational age.

Subjects will be recruited from well child visits at the Duke Primary Care offices at Brier Creek and Durham Pediatrics.

Subject Recruitment and Compensation

Subjects will be recruited directly by pediatrician during well-child checks between the ages of 2 months and 12 months. Pediatricians at the Duke Primary Care offices at Brier Creek and Durham Pediatrics will be informed of the study so they can also discuss it with eligible patients. The area served by this office has a heterogeneous demographic.

Approximately 25 subjects will be recruited. Subjects will not receive any compensation for participation in the study.

Consent Process

Consent process will be conducted by PI and/or CRC. Parents or legal guardian will provide consent. The consent process will take place via Duke-licensed Zoom software, which establishes a secured telecommunication portal. We will not enroll subjects whose parents are unable to provide legally effective consent. The consent form will be in English. E-consent through REDCap will be used.

Study Interventions

The smart mattress device would work by detecting when a child is awake using two sensors, an accelerometer and a microphone. When awake and crying, the device would produce a sound and gentle internal vibration to soothe the child back to sleep (thereby creating a new sleep association). Based on data from previous nights, the internal algorithm of the device will eventually switch modes into a "sleep training" mode. In this mode, the device will wean the child off of this new association by decreasing the output from the device gradually over the course of weeks. This would slowly teach a child to self-soothe, thereby allowing for more continuous sleep.

Risk/Benefit Analysis

The risks for participation are minimal. There is potential risk of worsening of sleep during the course of the study. For example, the infant has to sleep on a new surface or does not soothe with the motion and sound produced, thereby worsening sleep. As far as risks from the electronics of the device itself, the device uses off-the-shelf electronics and power supply that pose minimal risk, as these components undergo safety testing prior to commercialization. Benefit includes potential to improve the child's sleep by eliminating sleep associations.

Cost to Subject

There will be no costs associated with participation in this study.

Data Analysis and Statistical Considerations

The proposed study design was discussed with a biostatistician to determine goal enrollment. Power analysis to achieve an *a priori* confidence level of 80% was evaluated for a variety of metrics. Since we do not have a pilot study to determine standard deviation (SD) of metrics to be measured, we determined SD by dividing approximate range in each metric by 5. Paired T-tests will be used for analysis. For the following metrics, an N of 20 is necessary:

1. Number of total discrete crying episodes
2. Number of discrete crying episodes between time asleep and time awake

Power Calculation:

Power	N	δ1	σ	Size	Alpha	Beta
0.80729	20	2.0	3.0	0.667	0.050	0.19271

For the following metrics, an N of 14 is necessary:

1. Number of minutes of crying at night (total)
2. Number of minutes of crying between time asleep and time awake
3. Number of minutes of quiet wakefulness

4. Number of minutes of quiet wakefulness between time asleep and time
5. Number of minutes of wakefulness
6. Number of minutes of wakefulness between time asleep and time awake

Power Calculation:

Power	N	δ1	σ	Size	Alpha	Beta
0.82156	14	10.0	12.0	0.833	0.050	0.17844

For the following metrics, an N of 12 is necessary:

- A. Total length of time asleep
- B. Total length of time in bed

Power Calculation:

Power	N	δ1	σ	Size	Alpha	Beta
0.83997	12	45.0	48.0	0.938	0.050	0.16003

Ineligible subjects will be withdrawn from statistical analysis. Estimated accrual rate is 5 subjects per month. Target accrual is 25 subjects (assuming 20% drop out with goal of 20 subjects that complete the study). Time to target accrual is 5 months.

Data and Safety Monitoring

There are unlikely to be any adverse events for this study. The principal investigator and study coordinator will monitor data and study participant safety. Participants will have the phone number and email address for research study staff to report any areas of concern.

The study coordinator will collect, enter, and complete a quality check on study data each month. Data will be stored in REDCap database.

Study discontinuation:

Patients will be discontinued if there are significant adverse effects that are judged to outweigh possible benefits. Risk of such events is low given the nature of this device.

Adaptations to COVID-19

Participants for the study will be recruited during already scheduled well-child check-ups from our Duke Primary Care Pediatric practice at Brier Creek and Durham Pediatrics. The caregiver will be interviewed via videoconference to ensure the child meets eligibility criteria. Consent will also be performed via teleconference, and the mattress will be delivered directly to the participants with minimal direct interaction. Collection of the mattress will be arranged without face-to-face interaction and each mattress will be sterilized prior to reuse. Data analysis will be performed remotely.

References

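### Adverse events are collected only through parent-initiated contact and two unscripted calls, with no recorded safety query and no call scheduled between Day 15 and Day 30

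*Combined protocol and SAP*

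**What the plan says.** The Data and Safety Monitoring section states "There are unlikely to be any adverse events for this study". It assigns responsibility ("The principal investigator and study coordinator will monitor data and study participant safety") and gives one reporting route: "Participants will have the phone number and email address for research study staff to report any areas of concern". It also provides for a monthly collection and quality check of study data. It contains no adverse-event definition, query, form or within-participant review schedule.

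The Schedule of Events adds two contacts started by staff. The Day 5 contact is a "check-in call from study team to ensure everything going well and answer any questions". The next reads "Day 15 of study – check-in call from study team to answer any questions". On Day 30 the mattress is returned and parents complete the closing questionnaire.

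The Risk/Benefit Analysis names one main hazard: "There is potential risk of worsening of sleep during the course of the study". It also discusses the electronics, which it rates as minimal risk. Under Study discontinuation the rule is: "Patients will be discontinued if there are significant adverse effects that are judged to outweigh possible benefits".

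Device metrics are held on a micro SD card. Parent-reported metrics are taken at baseline and end of study. Study Interventions says that the device will at some point enter a mode that reduces its output over weeks, and gives no study day for the switch.

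**The concern.** The discontinuation rule and any safety statement in the final report both depend on the study team learning of events. The plan describes opportunities for parents to mention a problem. It does not describe a question put to every family in the same way, with the answer written down. Without a recorded answer, a family that had no problem cannot be told apart from one that was not asked or did not volunteer it.

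The participants are infants aged 2 to 12 months using a novel device that vibrates and makes sound. Two gaps matter most. First, events other than poor sleep, and the reason a family stopped using the mattress, have no listed place in the data. Second, nothing scheduled between Day 15 and Day 30 would bring worsening sleep to the team's attention while the infant is still on the mattress.

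**Working it through.** **The plan's own figure.** The safety section gives no rate or target. The relevant figures are in Data Analysis and Statistical Considerations: 20 completers and 20% dropout. 20 / (1 − 0.20) = 25, which matches the stated accrual. Expected dropouts are 25 − 20 = 5.

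**Contact schedule.** The scheduled study days are 1, 5, 15 and 30. The gaps are 5 − 1 = 4, 15 − 5 = 10 and 30 − 15 = 15 days. The last gap is the longest and contains no staff call. The data check is monthly and participation lasts about 30 days, so that check cannot serve as monitoring within a participant.

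**What the documents describe for each kind of information.**

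| Information | Days 5 and 15 | Between Day 15 and Day 30 | Day 30 |
|---|---|---|---|
| Worsening sleep | May come up on a call; no query or record stated | Logged on the SD card; no review described; parent may phone or email | Parent ratings; SD card returned with mattress |
| Device fault, medical contact, other health concern | May come up on a call; no query or record stated | Parent may phone or email | No listed item |
| Use stopped, and why | No listed item | No listed item | No listed item |

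The first row shows late review of data that are collected. The second and third rows show information with no defined collection.

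**Weaning and the 15-day gap.** The start day is not given, so overlap can only be shown under assumptions. If weaning lasts at least 14 days and starts on Day 3 or later, it runs to Day 16 or beyond and part of it falls after the last call. If it starts earlier or is shorter, the Day 15 call may cover most or all of it. If it starts around or after Day 15, it falls in the gap.

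**Illustration of incomplete reporting.** Suppose each of n = 25 infants independently has an event with probability p, and each event is reported with probability s. The chance of at least one recorded event is 1 − (1 − p·s)^25. With p = 0.10:

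- s = 1: 1 − 0.90^25 = 0.928
- s = 0.5: 1 − 0.95^25 = 0.723
- s = 0.3: 1 − 0.97^25 = 0.533

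Both p and s are assumptions; the documents give neither. The figures apply to events that depend on volunteered reports. They do not apply to worsening sleep among completers, because every family is asked about sleep at the end of study.

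**The case against.** The strongest reply is that the plan is not passive. Staff call every family twice, and the Day 5 call is expressly to see that all is going well. Named staff are responsible for safety. Worsening sleep is close to the efficacy outcome itself: parents rate crying, crib removals, sleep length and sleep quality at both ends, and the device logs crying, wakefulness, time asleep and latency. For a study of about 25 infants over 30 days that the protocol rates as minimal risk, this may be thought proportionate.

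Much of this stands, and it rules out several stronger readings that a reader might infer:

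- That safety rests on parents phoning or emailing alone. The two staff calls contradict this, although they have no stated script or record.
- That worsening sleep would go undetected. In completers it is measured by Day 30; the shortcoming is that no earlier review is described.
- That weaning takes place in the final 15 days. The documents give no start day.
- That worsening sleep is the only risk considered. The electronics are discussed too.
- That no events in 25 infants, which excludes only true rates above 1 − 0.05^(1/25) = 11.3% (one-sided 95%), is evidence of this defect. That bound follows from the sample size even with complete capture, and better recording would not change it.

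The reply does not cover events other than sleep, or families who leave. The sleep metrics cannot register a device fault or a medical contact. Families whose infants slept worse could be among the 5 expected dropouts, and Day 30 data may be missing for exactly those families. That last step is a possibility; the documents do not establish it.

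**Conclusion.** The point holds as a gap in how adverse events are asked about and recorded. The two calls have no stated event query or record. Events other than sleep, and reasons for stopping, have no listed item. No sleep data are described as reviewed before Day 30, and the final 15 days have no scheduled call. It is a cheap improvement that should be made, and it does not affect the efficacy analysis or the sample size.

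Its numerical size cannot be fixed from the documents. The fall from 93% to 72% or 53% shows how incomplete reporting could matter in a sample of 25, but it depends on an assumed 10% event rate and assumed reporting fractions of 50% and 30%. The conclusion itself does not need those figures; it rests on what the safety section, the schedule and the metric lists describe.

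**What to change.** Add one short scripted safety query, worded identically each time, to the Day 5 call, the Day 15 call and the Day 30 questionnaire. It should ask whether sleep is worse than before the mattress, whether the device has had a fault, whether there has been any other health concern or medical contact, and whether use has stopped and why. Record every answer in REDCap, including none, and report the counts with the number of families asked at each contact.

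The cost is a few minutes at three existing contacts and one REDCap form, with no new visits.

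The change has a limit that the protocol should acknowledge. The Day 30 query picks up late events only in retrospect, so detection between Day 15 and Day 30, while the infant is still on the mattress, would continue to depend on parents making contact.
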